7.8 Trial Closure

Trial enrolment may be stopped at a trial site when the total requested number of patients for the trial has been obtained. PIs will be informed by the LCTC when patient recruitment is to cease. A letter to patients to inform them of the study results will be provided to sites to distribute by post.

Otherwise, the end of the trial is defined to be the date on which data for all participants is frozen and data entry privileges are withdrawn from the trial database after the last follow up visit of the last patient recruited (21 - 28 days after recruitment (+4 days depending on surgery)). However, the Trial Steering Committee (TSC) may recommend that the trial be stopped prematurely. Such premature termination or suspension of the trial will be notified to the MHRA and REC as required. Ongoing patients must be contacted to notify them of the end of the study.

8 TRANSLATIONAL RESEARCH

The collection of biological material is a key part of this study and will enable translational research. All EMERALD samples should be collected, processed, stored and shipped as detailed in the EMERALD Laboratory Manual provided to sites. Sampling kits will be provided and postage costs will be covered by the trial.

8.1 Blood (Plasma & Serum) Collection

In addition to the patient's routine haematology blood samples, a further 20ml (approximately) of blood will be taken, at specified time points throughout the study.

These samples will be processed at each trial site, stored at -80°C and then transferred in batches to the Liverpool GCLP Facility, University of Liverpool. Samples will then be stored under appropriate conditions for up to 10 years from study start and will be used in future translational studies subject to ethical approval.

Blood samples for translational research must be taken at the Baseline (Visit 1) and Tissue Collection Visit (Visit 2). If a patient is deemed too unwell to receive treatment, every effort should still be made to take the samples.

A separate translational plan will be completed detailing analysis of samples. A laboratory manual will be provided to site on collection procedures and transferring samples to Liverpool before the trial begins at each site.

8.2 Formalin Fixed Paraffin Embedded Tissue of Breast

FFPE tissue of breast will be taken at the pre-planned Tissue Collection Visit (Day 14(+4)) as part of surgery (ideally a core biopsy of the resected tumour tissue) or as a research core biopsy. The cores should be put in formalin and a trial specific FFPE block created for the primary endpoint analysis.

FFPE tissue remaining from the diagnostic core biopsy will be requested immediately upon randomisation and sent to the Liverpool GCLP Facility at the same time as the surgical sample or as soon as possible thereafter.

FFPE blocks created as part of standard care from the resected tumour tissue will also be requested for the trial.

For patients whose samples had AR staining performed, but who were not consented or entered onto the study, a member of their direct care team will remove all identifiable information from their diagnostic biopsy FFPE block and standard care surgery FFPE block. The blocks will be sent to the University of Liverpool GCP Laboratory (the block numbers will remain on the FFPE blocks and they will be sent with a sample information sheet containing the patient's screening number and the block number). The pathology report for the diagnostic block and standard care surgery block will also be anonymised and uploaded to the LCTC portal.

8.3 AllProtect® Sample

A fresh sample of tumour tissue (not placed in formalin) will be collected at the pre-planned Tissue Collection Visit (Day 14 (+4)) as part of surgery (ideally a core biopsy of the resected tumour tissue) or as a research core biopsy. This sample should be taken by the surgeon following surgery or by the pathologist when they receive the resected tumour tissue and should be stored in an AllProtect® tube and frozen at -80°C.

If it is not possible, due to local procedures, to take the AllProtect Sample then an agreement can be made and filed with the EMERALD Trial Team to not collect this sample.

8.4 Summary of Collection of Biological Material for Translational Research (Table 3)

Sample to be collected	Visit 1 (Baseline)	Visit 2 (Pre-Surgical/ Surgery)	Visit 3 (End of Study/Follow Up)
Time Point	Day 0	Day 14 +4 days	Day 21- 28
Plasma & serum samples	X	X ¹	
FFPE tissue of breast		X	
AllProtect® sample		X	
FFPE tissue remaining from diagnostic core biopsy	Samples are requested following randomisation and sent to the Liverpool GCLP Facility after the patient's pre-planned surgery visit.		

¹Samples to be taken from patients within 24 hours of last dose of IMP

9 TRIAL TREATMENT

9.1 Introduction

Patients will be randomised 3:1 to 9mg of enobosarm (therapeutic arm) to a control arm receiving “treatment as usual” with no placebo. Enobosarm will be taken orally, once daily, up to surgery/neoadjuvant chemotherapy/endocrine therapy which should take place 14 days +4 days from commencing treatment. Enobosarm will be prescribed in hospital and is self-administered at home by the patients. Patients will be dispensed two bottles containing 35 enobosarm softgels (enough in each for a 7 day course +4 days/wastage) at Visit 1 (Baseline). Compliance to treatment will be checked through a patient drug diary on Day 14 (Visit 2) hospital visit. Remaining unused enobosarm will be collected and accounted for at Visit 2.

9.2 Enobosarm

9.2.1 Formulation, Packaging, Labelling, Storage and Stability

GTx-024 3.0mg softgels will be supplied as opaque, white to off-white, size 5, oval softgel capsules with “GTx” imprinted in black ink on the outer shell containing 3.0mg of GTx-024. The liquid softgel fill is composed of GTx-024 dissolved in polyethylene glycol 400.

GTx-024 3.0 mg softgels will be packaged in high density polyethylene (HDPE) bottles with induction seal and child-resistant closure. Each bottle will contain thirty-five (35) GTx-024 3.0 mg softgel capsules. Two (2) 35-ct bottles will be packed into a single kit carton, with each kit carton containing sufficient drug supply to cover the 14 days +4 days dosing period with overage. Patients will be prescribed two bottles at baseline, patients will be requested to return both bottles at Visit 2 on Day 14(+4).

Each bottle and each kit carton will be labeled with dosing and storage instructions.

Enobosarm (GTx-024) should be stored at room temperature, 15°C to 25°C (59°F to 77°F), with excursions permitted to 30°C, and protected from moisture. Stability will be confirmed for at least the length of the clinical trial or new material will be manufactured and supplied. The expiry date of the study drug will be on each bottle.

9.2.2 Dosage and Administration of Study Treatment

One daily dose of 9mg enobosarm (3x3.0mg softgels) will be taken orally with water and with food where possible at approximately the same time each day. Patients will be asked to commence the enobosarm at a time convenient to them on Day 1 and to attempt to keep this time consistent.

9.2.3 Dose Modifications

No dose modifications are allowed as part of study given the short duration.

9.2.4 Accountability Procedures for Study Treatment

The PI is responsible for the correct storage of study medication according to GTx, Inc. recommendations outlined in the Investigator's Brochure. The study medication made available for this clinical trial must be used in accordance with the protocol and dispensed only under the supervision of the Investigator and documented sub-Investigators. The Investigator must maintain complete and accurate records, showing the receipt and disposition of all supplies of the study medication delivered by the GTx, Inc., authorized representative. These records must include a master record which lists the date of receipt of all study medication shipments, batch numbers, expiration date, and quantities received. In addition, a dispensing record which includes all quantities dispensed, identification of the person to whom study medication was dispensed, the date of each dispensing, and the identification of the dispenser will also be maintained. The master dispensing records are separate from records kept for individual trial patients.

It is the Investigator's responsibility to ensure that study medication used by trial patients plus unused study medication equal the total amount received from the GTx, Inc. authorized representative. Damaged and/or contaminated packets must also be accounted for in the dispensing records. All discrepancies must be explained in writing. The study personnel responsible for study medication administration to the patient will record the date and time the initial treatment is given to the patient. In addition, the Drug Accountability electronic case report form (eCRF) will document any treatment interruptions or discontinuations.

9.2.5 Assessment of Compliance with Study Treatment

Patients should be instructed to return all unused study medication and containers at Visit 2 prior to surgery/commencing neoadjuvant chemotherapy or endocrine chemotherapy so that drug accountability can be performed. If the patient forgets to bring the bottle with them, they will be able to bring the bottle back at the next visit (Visit 3 for follow-up). The research nurse is required to count all returned study capsules and record this on the eCRF, a reason must be provided for any missing or damaged study drug. The dispensing pharmacy should also count returned study capsules and record this on the drug accountability log.

All study medication returned by patients must be accounted for and verified by the EMERALD Trial Coordinator. After verification of study medication, a drug destruction form should be completed and sent to the EMERALD Trial Coordinator who will then authorise the destruction of returned, damaged and unused study medication according to local pharmacy SOPs.

9.3 Concomitant Medications/Treatments

Forbidden medications and treatments during the study include:

- Major surgery within 28 days before randomization
- Testosterone, methyltestosterone, oxandrolone (Oxandrin®), oxymetholone, danazol, fluoxymesterone (Halotestin®), testosterone-like agents (such as dehydroepiandrosterone, androstenedione, and other androgenic compounds,

including herbals), or antiandrogens. Previous therapy with testosterone and testosterone-like agents is acceptable with a 28-day washout (if previous testosterone therapy was long-term depot within the past 6 months, the site should contact the Medical Monitor). Treatment with any of the following hormone replacement therapies, unless discontinued at least 28 days prior to randomization

- Oestrogens
- Megesterol acetate
- Treatment with any investigational agent within <4 half-lives for each individual investigational product OR within 28 days prior to randomization
- All other anticancer treatments (including, but not limited to, all SERMs, AIs, and fulvestrant)
- Caution should be exercised when administering potent CYP3A4 inducers, UDP inhibitors, and substrates of BCRP with GTx-024. Drug-drug interaction studies conducted with GTx-024 3mg have demonstrated that concomitant use of CYP3A4 inducers may decrease the rate and extent of exposure of GTx-024 and its glucuronide metabolite. UDP inhibitors may increase GTx-024 and glucuronide exposure. Concomitant administration of GTx-024 with BCRP substrates may lead to increased exposure of the BCRP substrate.

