The relative contributions of various cytochrome P450 isoforms to the oxidative metabolism of enobosarm were investigated through *in vitro* incubations with recombinant human CYP1A2, CYP2C9, CYP2C19, CYP3A4, and CYP2D6. Incubation of enobosarm with CYP3A4 and CYP2C19 produced very small amounts of singly oxidized metabolites, while incubations of enobosarm with CYP1A2, CYP2C9, and CYP2D6 resulted in no detectable metabolites. These results suggest that cytochrome P450-mediated oxidation is a relatively minor pathway for enobosarm metabolism.

Phase II metabolism of enobosarm was evaluated in human liver microsomes and S9 fraction and with recombinant human UDP-glucuronosyl transferase (UGT) isoenzymes. Incubations of GTx-024 with UGT1A1 and UGT2B7 showed an increase in the glucuronide metabolite, whereas UGTs 1A4, 1A6, 1A8, 1A10 and 2B15 did not generate the glucuronide product. These *in vitro* results suggest that UGT1A1 and UGT2B7 might be the primary UGT isoforms responsible for the Phase II biotransformation of enobosarm *in vivo*.

Inhibition of Human Liver Microsomal CYP450 Isoforms

The ability of enobosarm to inhibit the activity of individual cytochrome P450 enzymes 1A2, 2C9, 2C19, 2D6, and 3A4 was evaluated using human recombinant CYP450 isozymes. Enobosarm significantly inhibited CYP450 2C19 and 2C9 with an IC₅₀ of approximately 0.7 and 1.6 μ M, respectively, but did not appreciably inhibit the other P450 enzymes tested over the range of 0.15 to 20.0 μ M. Studies using human liver microsomes indicated that enobosarm is only a moderately weak inhibitor of CYP2C19 with a K_i of 8.9 μ M. Based on the cumulative *in vitro* data (IC₅₀ and K_i) for enobosarm against CYP2C9 and 2C19, the probability of any clinical drug:drug interaction in patients administered GTx-024 at doses of up to 3mg would be considered remote, while a drug:drug interaction with a CYP2C9 substrate or inhibitor may be possible at a dose of 9mg.

Induction of CYP450 Isoforms in Human Primary Hepatocytes

An increased activity was noted for CYP3A4 when incubated with enobosarm, with an IC₅₀ >10 μ M. The activities of CYP2D6 and 1A2 were not affected by 10 μ M enobosarm.

Pharmacokinetics (PK)

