In a drug-drug interaction study in healthy male volunteers (protocol G100512), a single 3mg oral dose of enobosarm was administered either alone or after repeated daily doses of 200mg itraconazole, (CYP3A4 inhibitor). Mean maximum (based on C_{max}) and overall (based on AUC_{0-t} , AUC_{0-24} , and AUC_{∞}) of plasma enobosarm exposures following a single dose of enobosarm were not affected by co-administration of itraconazole. Median T_{max} and mean $T_{1/2}$ values of enobosarm were also similar following enobosarm alone or in combination with itraconazole. Similarly, PK of plasma enobosarm glucuronide were not affected by co-administration of itraconazole.

In a drug-drug interaction study in healthy male volunteers (protocol G100513), a single 3mg oral dose of enobosarm was administered alone or after repeated daily doses of 600mg rifampin, (CYP3A4 inducer). Co-administration of enobosarm with rifampin lowered the peak concentrations and exposure to enobosarm by all measures. The mean plasma C_{max} value for enobosarm following administration of enobosarm and rifampin was 22% lower compared to that observed following administration of enobosarm alone. Mean plasma AUC_{0-t} , AUC_{0-24} , and AUC_{∞} for enobosarm were also lower (approximately 30 to 45% lower) when enobosarm was co-administered with rifampin relative to when enobosarm was administered alone. Median T_{max} following administration of enobosarm and rifampin occurred approximately 1 hour later and mean $T_{1/2}$ more than 5 hours shorter when compared to when enobosarm was administered alone. Similarly, peak concentrations and exposure to enobosarm glucuronide were lower by all measures when enobosarm was co-administered with rifampin.

In a drug-drug interaction study in healthy male volunteers (Protocol G100514) a single 200mg oral dose of celecoxib (CYP2C9 substrate) was initially administered alone, followed by a single 200mg oral dose of celecoxib with repeated daily doses of enobosarm 3.0mg. Multiple doses of enobosarm did not affect the single-dose PK of oral celecoxib. A single dose of celecoxib did not affect the multiple-dose PK of enobosarm and enobosarm glucuronide. These results suggest that there is no DDI between celecoxib and enobosarm.

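### Section 9.3 omits CYP2C9 substrates from its co-medication caution, although section 2.1 says a CYP2C9 interaction may be possible at 9 mg, the trial dose

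*Protocol*

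**What the plan says.** Section 9.3 of the protocol is the instruction to sites on co-medication. After the forbidden treatments it adds a caution: "Caution should be exercised when administering potent CYP3A4 inducers, UDP inhibitors, and substrates of BCRP with GTx-024". The evidence it gives begins "Drug-drug interaction studies conducted with GTx-024 3mg have demonstrated", followed by one effect for each of the three named classes. CYP2C9 is not mentioned there, and Appendix 1 lists only CYP3A4 inducers.

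The trial dose is in section 9.2.2: "One daily dose of 9mg enobosarm (3x3.0mg softgels) will be taken orally".

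Section 2.1, under the heading on inhibition of CYP450 isoforms, reports work with recombinant enzymes: "Enobosarm significantly inhibited CYP450 2C19 and 2C9", with IC50 values of about 0.7 and 1.6 µM respectively. It then judges the clinical relevance by dose. For the lower dose, "the probability of any clinical drug:drug interaction in patients administered GTx-024 at doses of up to 3mg would be considered remote". The sentence goes on: "while a drug:drug interaction with a CYP2C9 substrate or inhibitor may be possible at a dose of 9mg".

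Under Pharmacokinetics, section 2.1 describes the celecoxib study (G100514), in which celecoxib was given alone, "followed by a single 200mg oral dose of celecoxib with repeated daily doses of enobosarm 3.0mg". It found no effect in either direction.

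**The concern.** The background names one interaction that it considers possible at the trial dose and remote at 3 mg. The operative section draws its list from 3 mg studies and leaves that interaction out. A site following section 9.3 would take extra care with three classes, but not with the only class that the protocol links expressly to 9 mg.

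What is at stake is the safety of a patient already taking a drug cleared by CYP2C9. If enobosarm at 9 mg inhibits that enzyme to a relevant degree, exposure to the other drug could rise during the two weeks or so before surgery or neoadjuvant treatment. The efficacy comparison is not at stake.

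**Working it through.** No figure in the plan needs reproducing. The check sets the statements side by side and counts which studies bear on the question.

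**1. The interaction studies in section 2.1 (Pharmacokinetics), all with enobosarm 3 mg**

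| Study | Partner drug and role given | Direction tested | Result | Class in the 9.3 caution? |
|---|---|---|---|---|
| G100512 | Itraconazole, CYP3A4 inhibitor | Partner on enobosarm | No effect | No |
| G100513 | Rifampin, CYP3A4 inducer | Partner on enobosarm | Lower enobosarm exposure | Yes |
| G100514 | Celecoxib, CYP2C9 substrate | Mainly enobosarm on partner | No effect | No |
| G100515 | Probenecid, UDP glucuronosyl transferase inhibitor | Partner on enobosarm | Higher enobosarm AUC | Yes |
| G100516 | Rosuvastatin, BCRP substrate | Mainly enobosarm on partner | Higher rosuvastatin exposure | Yes |

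The three classes in section 9.3 are exactly the three that were positive at 3 mg.

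**2. Counts**

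- Studies of repeated enobosarm on another drug, the direction that matters for substrates: 2 of 5.
- Studies with a CYP2C9 substrate: 1 of 5 (42 healthy males, Table 1).
- Studies at 9 mg: 0 of 5.

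**3. Dose gap**

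Studied dose / trial dose = 3 mg / 9 mg = 1/3.

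Section 2.1 describes single-dose kinetics as linear and proportional over 1 to 100 mg. For repeated dosing it says only that exposure rose with dose. If proportionality carried over to repeated dosing (an assumption), exposure at 9 mg would be about 9/3 = 3 times that at 3 mg.

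**4. Does the negative celecoxib study close the question?**

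Section 2.1 makes two statements: remote up to 3 mg, and possible at 9 mg. The celecoxib study was run at 3.0 mg. Its result agrees with the first statement and does not test the second.

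**5. Substrates, inhibitors or both?**

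Section 2.1 names both. A CYP2C9 inhibitor could raise enobosarm only if CYP2C9 metabolised it. Under Drug Metabolism the protocol reports that "incubations of enobosarm with CYP1A2, CYP2C9, and CYP2D6 resulted in no detectable metabolites". The inhibition finding supports a concern about substrates. Nothing in the protocol gives a mechanism for inhibitors.

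**6. Can the effect be sized?**

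No. A first estimate would need a plasma concentration at 9 mg to set against the IC50 of about 1.6 µM, and the number of patients taking CYP2C9 substrates. The protocol gives neither.

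**The case against.** The best reply is that section 9.3 follows a coherent rule: it lists classes that showed an effect in people. CYP2C9 was tested clinically and was negative, as was itraconazole, and neither is listed. Nothing in section 9.3 is false, and it does not claim to be complete. That makes this an omission rather than a contradiction. The rule still fails for this item, because a list of 3 mg positives cannot contain a risk said to arise only above 3 mg.

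The in vitro evidence is also softer than the recombinant figures suggest. In human liver microsomes the drug was only a moderately weak CYP2C19 inhibitor (Ki 8.9 µM, against a recombinant IC50 of about 0.7 µM). No such value is given for CYP2C9, so the 1.6 µM figure may overstate inhibition. That limits severity, but section 2.1 reached its 9 mg statement with both kinds of data in view.

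Section 2.1 refers readers to the Investigator's Brochure for more on metabolism, and section 3.1 requires sites to acknowledge receipt of it. The brochure may cover CYP2C9, but it is not available here, and it would not reconcile two parts of the same protocol.

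Existing safeguards count. Co-medication is recorded at all visits (section 7.6.2) and changes are checked in the Day 7 call (section 7.2.1). Clotting and liver tests are done at screening, baseline and Visit 2 (Table 2 in section 7.2), and the investigator judges bleeding risk (section 5.2, criterion 9). However, recording a drug does not tell a site that its class needs care, and no routine blood test falls between baseline and Visit 2.

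Finally, the caution prescribes no specific action, so adding a class triggers none. That is true, and it is a further reason to call the point minor.

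**Conclusion.** The concern holds, at minor severity. The protocol states a possible CYP2C9 interaction at its own dose and does not carry it into the co-medication guidance. That guidance rests on studies at one third of the trial dose, and none of the five was done at 9 mg.

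The conclusion rests on the protocol text alone. It assumes that the 9 mg statement in section 2.1 is still the sponsor's view. It does not assert that a clinically relevant interaction occurs: the signal is in vitro, worded as a possibility, and cannot be sized from the document. Dosing normally lasts 14 to 18 days. The sample size, the primary analysis and the interpretation of Ki67 are unaffected.

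**What to change.** Add CYP2C9 substrates to the caution in section 9.3. Extend the existing reference to 3 mg studies by saying that this is one third of the trial dose and that the CYP2C9 question has not been tested at 9 mg. Do not carry over the reference to CYP2C9 inhibitors, for which the protocol gives no mechanism.

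Alternatively, if the sponsor considers the 9 mg statement in section 2.1 superseded, correct it there and leave section 9.3 as it is. Either route makes the two sections agree. How co-medicated patients are then managed is for the sponsor to decide.

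The cost is one sentence and a short memo to sites. The only downside is closer review of a few co-medicated patients.

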9.4 Missed Dose and Vomiting Post Dose

If a dose is missed, enobosarm should be taken immediately and continue on the following day with the once daily dose as recommended. The dose should not be doubled within the same day to make up for a missed dose. Missed doses should be recorded in the patient drug diary along with the time and date of the next dose.

If a patient vomits within 6 hours of dose, they should take another complete dose (3 x 3.0mg enobosarm Softgels).

